10.2 Immunogenicity Assessments

Blood samples for immunogenicity assessments (ADA) will be collected at the time points shown in [Appendix 2](#).

10.3 Pharmacodynamic Assessments

10.3.1 Receptor Occupancy and/or T-cell Binding

The receptor occupancy of MGD014 binding sites on CD3-expressing T cells in peripheral blood will be estimated. The percentages of T cells in peripheral blood with MGD014 bound will be measured.

% RO = $(MFI \text{ of anti-MGD014 events with saline}) / (MFI \text{ of anti-MGD014 events with excess MGD014}) \times 100$. An event is defined as either a CD4-expressing or CD8-expressing T cell that has MGD014 binding to the T cell as detected by an anti-MGD014 antibody.

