2.2.1 MGD014 Nonclinical Pharmacology

A brief summary of MGD014 nonclinical pharmacology data is provided below; please reference the **MGD014 Investigator's Brochure (IB)** for a more detailed description.

Binding of MGD014 to its target antigens, HIV-1 env and human CD3, was characterized in vitro by both surface plasmon resonance (SPR) analysis and flow cytometry. SPR analysis using recombinant soluble human antigens revealed MGD014 binds with K_D values of approximately 6.9 nM to CD3 and with subnanomolar (<1 nM) K_D values to HIV-1 env. Like the parent A32 antibody, MGD014 binding to HIV-1 env was enhanced in the presence of soluble CD4 protein, which is known to trigger conformational changes in HIV-1 env proteins. Flow cytometry analyses confirmed the ability of MGD014 to bind natively expressed cell surface CD3 on human T cells, as well as to cell surface HIV-1 env on human cell lines engineered to express HIV-1 gp140 or gp160 or on human CD4 cells infected by HIV-1 isolates. However, like the parental A32 antibody, MGD014 was inefficient at binding HIV-1 virions, indicating that MGD014 selectively recognizes the env antigen structures expressed on the surface of HIV-1 infected cells.

[figure not shown]

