with potentially reduced penetrance by MGD014 [38, 39]. For example, there is increasing evidence that the brain harbors latent HIV-1 infected cells capable of being reactivated [37, 40, 41, 42], and it may be particularly challenging for MGD014 to gain access to the CNS due to the limits imposed by the blood-brain-barrier (BBB). T cells are capable of trafficking to the CNS [43, 44] and are known to be present in the cerebral spinal fluid (CSF) of both seronegative individuals and PLWH [45, 46]. However, antibody molecules are only able to cross the BBB inefficiently; following IV infusion, CSF to serum concentration ratios of 1:200 to 1:800 have been reported [38, 39]. MGD014, which bears a mutated IgG1 Fc domain for extended serum half-life, would also be expected to cross the BBB inefficiently; thus, the higher serum concentrations resulting from the higher doses will favor the attainment of CSF concentrations that could enable MGD014-mediated targeted cytolytic activity in the CNS compartment.

In summary, MGD014 doses as high as 300 μ g/kg are expected to be adequately tolerated in PLWH on ART and capable of mediating activity against env antigen-expressing HIV-infected target cells, possibly even against those residing in ‘sanctuary’ compartments.

Table 1 MGD014 Dose Escalation Scheme

Cohort	Dose (μ g/kg)	C_{max} (ng/mL)	$C_{trough\ (7-day)}$ (ng/mL)	Theoretical RO at C_{max} (%)	Theoretical RO at $C_{trough\ (7-day)}$ (%)
1	0.1	1.7	0.27	0.2	0.03
2	0.3	5.2	0.8	0.7	0.1
3	1.0	17.2	2.7	2.2	0.3
4	3.0	51.5	8.0	6.3	1.0
5	10.0	171.7	26.8	18.2	3.4
6	30.0	515.1	80.3	40.0	9.4
7	100.0	1717.1	267.5	69.0	25.7
8	300.0	5151.4	802.6	87.0	51.0

Projected C_{max} and $C_{trough\ (7-day)}$ values were derived from allometric modeling of cynomolgus monkey PK data, using allometric exponents of 0.75 for clearance and 1.0 for volumes of distribution under the assumption of linearity to estimate PK in humans. Theoretical CD3 RO values were calculated from the Hill equation ($RO = [C] / (K_D + [C])$) using $K_D = 6.9$ nM for human CD3 binding.

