4.2.1 Dose Escalation Rules

Dose escalation from one dose cohort to the next dose cohort level depends upon the clinical safety profile (e.g., evaluation of AEs, VS, ECGs, and clinical laboratory parameters) of the dose administered up to and including the preceding dose cohort. Participants will not be dosed at the next higher dose level until all the safety data collected following each dose through Day 14 is reviewed by the principal investigator (PI) (or designee) in conjunction with the medical monitor and are determined to demonstrate acceptable safety and tolerability.

Dose escalation continues until the OBD is achieved, provided MTD is not exceeded. The PI (or designee) may also decide to halt dose escalation if, upon review of available RO data, the RO of CD3 is >95% in all participants within the dose cohort level, and further dose escalation is not expected to provide any additional biologic utility due to saturation of the CD3 receptor. There are three possible outcomes after the infusion of MGD014 in each dose cohort:

Scenario 1: No DLT is encountered, available data on binding to T cells shows CD3 RO is ≤ 95%. Dose escalation to next dose cohort occurs.

Scenario 2: No DLT is encountered, but available data on binding to T cells demonstrates CD3 RO is >95% in all participants at this dose level. Further dose escalation will halt, and study proceeds to Part 2, using the identified OBD dose.

Scenario 3: DLT is encountered in at least one participant. Dose cohort is expanded to an additional 3 participants. **Dosing of the first additional participant will be staggered**, so that the safety and tolerability of MGD014 is evaluated over the entire 2-week DLT in the first additional participant, at the dose in question, prior to dosing any additional participants at the same dose level.

- a. If the first additional participant does not experience a DLT during this 2-week DLT period, the 2 other additional participants can proceed to receive MGD014 at this dose level with a minimum of 24 hours between the dosing of each participant. If none of the 3 additional participants experience a DLT, dose escalation to the next dose cohort proceeds.

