4.11 Pharmacodynamic Endpoints and Analyses

Summary statistics for biomarkers, such as but not limited to those listed under **CP-MGD014-01 Protocol Section 10.3** and corresponding changes from baseline, will be summarized and may also be presented graphically as will possible associations between changes in PD measures of interest and MGD014 dose and exposure.

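### As written, the %RO formula subtracts no background and counts only MGD014-positive cells, so absolute receptor occupancy is biased upward when occupancy is low

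*Protocol*

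**What the plan says.** Protocol 10.3.1 gives an explicit calculation. The numerator is the MFI "of anti-MGD014 events with saline", the denominator is the MFI "of anti-MGD014 events with excess MGD014", and the ratio is multiplied by 100. Neither term has an isotype, unstained or pre-dose value subtracted. The cells that enter are defined as follows: "An event is defined as either a CD4-expressing or CD8-expressing T cell that has MGD014 binding to the T cell". A second measure is planned alongside, but it is not a term in the ratio: "The percentages of T cells in peripheral blood with MGD014 bound will be measured".

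RO is used in three places:
- Protocol 4.2.1 allows escalation to stop when "the RO of CD3 is >95% in all participants within the dose cohort level". This is an absolute value.
- SAP 4.11 refers to Protocol 10.3 for the biomarkers, says that summary statistics "and corresponding changes from baseline, will be summarized", and relates changes in PD measures to dose and exposure. It gives no RO formula of its own.
- Appendix 2 schedules RO before infusion in both parts, through Day 7 in Part 1, and before infusions 2 and 3 and at Day 77 in Part 2. A Part 2 footnote lets RO measurement stop in Step 3 once RO is no longer detectable.

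**The concern.** Background fluorescence adds to both the saline and the excess-MGD014 reading. In a saturated sample it hardly matters. In a sample with little drug bound, most of the numerator can be background. Counting only cells that already show MGD014 has a second effect in the same direction: unoccupied cells drop out of the numerator, while most T cells should qualify in the excess tube, so the two terms can describe different cells.

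What is at stake is the lower end of the RO data. Table 1 of the Protocol projects RO below 10% at Cmax in four of eight cohorts, and at 7 days in six of eight. Those absolute values, the trough samples in Part 2, and the judgement that RO has become undetectable all depend on a scale whose zero is not zero.

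**Working it through.** **Inputs.** The ratio and cell definition come from Protocol 10.3.1. Projected concentrations and RO come from Table 1 in Protocol 2.4.2, where "Theoretical CD3 RO values were calculated from the Hill equation". For affinity, Protocol 2.2.1 states "MGD014 binds with K_D values of approximately 6.9 nM to CD3". The molecular weight, 111.8 kDa, is in Protocol 2.2.2. The background share b (background MFI divided by saturated MFI) is not in the documents; I assume 1%, 5% and 10%.

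**1. Reproduce Table 1.** K_D = 6.9 nM × 111.8 kDa = 771.4 ng/mL, and RO = C/(771.4 + C). At 1.7 ng/mL this gives 0.22%, at 171.7 ng/mL 18.21%, and at 5151.4 ng/mL 86.98%. All eight Cmax values match Table 1 to rounding. (Protocol 2.4.1 gives the starting-dose RO at this Cmax once as 0.03% and once as 0.2%. The first is Table 1's trough value, and the passages should be reconciled. I use 0.2%.)

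**2. Can background be ignored?** The Protocol's own flow data in Figure 3 suggest not always. Control MFIs are 3235–3415, against 24850 (BaL) and 7967 (CH058). With controls subtracted the ratio is (24850 − 3235)/(7967 − 3235) = 4.6 to (24850 − 3415)/(7967 − 3415) = 4.7, consistent with the stated figure of about 5. Without subtraction it is 24850/7967 = 3.1. This is a different assay, so it does not supply b.

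**3. Formula as written, all cells counted.** Set saturated MFI to 1. The saline reading is then b + (1 − b)RO, so reported RO = RO + b(1 − RO).

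**4. Adding the positive-cell restriction.** This needs further assumptions: 400,000 simulated cells, log-normal background and specific signal (log SD 0.3 each), a positivity cut at the 99th percentile of background, and median MFI.

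| Dose (µg/kg) | Projected RO at Cmax, % | All cells, b = 1 / 5 / 10% | Positive cells only, b = 1 / 5 / 10% |
|---|---|---|---|
| Pre-dose | 0 | 1.0 / 5.0 / 10.0 | 2.2 / 10.8 / 21.5 |
| 0.1 | 0.2 | 1.2 / 5.2 / 10.2 | 2.2 / 10.8 / 21.5 |
| 1 | 2.2 | 3.2 / 7.1 / 12.0 | 3.2 / 10.9 / 21.6 |
| 3 | 6.3 | 7.2 / 10.9 / 15.6 | 7.2 / 12.1 / 21.9 |
| 10 | 18.2 | 19.0 / 22.3 / 26.4 | 19.1 / 22.5 / 27.5 |
| 300 | 87.0 | 87.1 / 87.6 / 88.3 | 87.1 / 87.7 / 88.3 |

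With background log SD 0.5, the pre-dose reading under the restriction is 3.6% at b = 1% and 36% at b = 10%. If strictly no cell passes the cut before dosing, pre-dose RO is undefined.

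The same formula applies at 7 days. At 30 µg/kg the projected 9.4% reads 9.4 + b × 90.6 = 10.3 / 13.9 / 18.5%.

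**5. Change from baseline.** With all cells counted, [b + (1 − b)RO] − b = (1 − b)RO. The offset disappears and a scale factor remains: 18.2% becomes 18.0 / 17.3 / 16.4%. Under the restriction the change is distorted the other way. At 10 µg/kg it is 19.1 − 2.2 = 16.9, 22.5 − 10.8 = 11.7, and 27.5 − 21.5 = 6.0 points, against 18.2. At 3 µg/kg it is 5.0, 1.3 and 0.4 points, against 6.3.

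**6. The 95% threshold.** A reported 95% corresponds to a true (0.95 − b)/(1 − b) = 94.95%, 94.74% or 94.44%.

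**The case against.** The strongest reply is that the planned analysis already deals with this. Every participant has a pre-infusion RO sample, PD changes from baseline are summarised, and it is changes that are related to dose and exposure. For the background term with all cells counted, that is right: only the factor (1 − b) remains. It does not hold for the positive-cell restriction (step 5), it fails if the pre-dose value is undefined, and absolute values are summarised as well.

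Second, the formula says MFI, not raw MFI. A correction might be in the Study Specific Laboratory Manual, which is not among the documents, and the Appendix 2 footnote on undetectable RO implies some rule separating signal from background. It is therefore not established that background will go uncorrected in practice. But neither the Protocol's description of the manual's content nor the footnote states a correction, and 10.3.1 sets out the calculation without one.

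Third, b may be small. Protocol 2.2.2 reports monkey binding as low as 1–2% of maximal, although without the method. That would favour the lower end of the range; at b = 1% a projected 0.2% still reads 1.2%.

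A reader might also infer that inactive cohorts will look active. The documents do not support that: the pre-dose sample carries the same floor, and in the simulation the 0.1 and 0.3 µg/kg readings barely differ from it.

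**Conclusion.** The point holds for absolute RO. Applied as written, Protocol 10.3.1 gives a positive or undefined pre-dose value and overstates low occupancy. The direction follows for any positive background. The size rests on an assumed b of 1–10% and, for the restriction to positive cells, on an assumed cut and spread. The bias matters for low-dose cohorts, Day 7 and trough samples, and for deciding when RO is undetectable.

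It should not be read as a threat to dose selection. The >95% criterion shifts by 0.05 to 0.56 points, and Part 2 is already fixed at 300 mcg/kg, which the Synopsis equates with the maximum administered dose. Nor is RO named in any study objective; the secondary PD objective concerns serum cytokines. The separately planned percentage of T cells with drug bound does not pass through this ratio.

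**What to change.** In Protocol 10.3.1 or SAP 4.11, before the RO analysis, define:

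%RO = (MFI saline − background) / (MFI excess MGD014 − background) × 100, over all CD4+ or all CD8+ T cells.

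Take background from a same-run negative control if there is one, and otherwise from the participant's pre-dose saline tube. Report the percentage of MGD014-positive T cells as a separate measure, as already planned. If the Laboratory Manual already specifies a correction, state it in the SAP.

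Pre-dose RO samples are already scheduled in both parts, so no new sampling is needed. The cost is re-computation, provided that the flow files are retained in a form that can be re-gated, which the documents do not say. Using the pre-dose tube brings in some between-run MFI noise. Low-dose RO values will become smaller.

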10.3.2 Serum Cytokine Analysis

Serum samples will be analyzed for concentrations of serum cytokines, which will include, but not be limited to, IFN- γ , IL-2, IL-5, IL-6, IL-10, and TNF- α .

10.3.3 T cell Phenotype and Function

Flow cytometry panels for T cell phenotyping will include: T cell subsets, surface expression levels of activation of T cells, and exhaustion of T cells. Functional changes to circulating CD8 T cells by flow cytometry may be assessed.

11 ASSESSMENT OF EFFICACY

11.1 Efficacy Assessments

Efficacy will be assessed by examination of the ability of MGD014 administration to alter markers of persistent HIV-1 infection in individuals on ART if the participant consents to the optional leukapheresis through evaluation of: a) the frequency of resting CD4 T cell infection by QVOA and b) levels of plasma HIV-1 RNA, as measured by SCA.

11.1.1 Resting CD4 T Cell Infection

Lymphocytes by continuous-flow leukapheresis (samples obtained as per [Appendix 1](#)) and resting CD4 T cells are isolated as previously described [\[52\]](#).

Quantitative viral outgrowth assay measurements determine the frequency of CD4 resting cell infection, expressed as infectious units per million (IUPM). The resting cell infection frequency is a measure of the lowest detectable HIV reservoir. A statistically significant decline in the HIV reservoir would be considered evidence of a reduction in the HIV reservoir.

11.1.2 Plasma for SCA

Residual low-level HIV-1 viremia by SCA, as evidence suggests that such HIV-1 viremia originates in persistently infected cells, and low-level HIV-1 viremia might be reduced by an augmented antiviral immune response.

12 ADVERSE EVENT REPORTING AND ASSESSMENT OF SAFETY

The safety assessment will be based on the evaluation of all AEs that occur from the time of initiation of administration of study drug through the End of Treatment Visit or 30 days after the last dose of study drug (whichever is later) and will be determined based on signs, symptoms, physical examination findings, and/or laboratory test results from enrolled participants, as appropriate.

If an AE occurs, the study coordinator, in collaboration with the PI, will evaluate the severity and seriousness of the AE and the relationship to the study drug, and will document the findings.

All adverse events will be graded according to the Division of AIDS Table for Grading the Severity of Adult and Pediatric Adverse Events, corrected Version 2.1, July 2017, which can be found on the DAIDS Regulatory Support Center Web site: <http://rsc.tech-res.com/clinical-research-sites/safety-reporting/daids-grading-tables>.

AEs reported between the time the potential participant signs the informed consent form (ICF) and the administration of the first dose of study drug will be captured as medical history unless the AEs are attributed to protocol-specified procedures that are not part of standard of care that occur during this time period, in which case the AEs will be collected on the Source Document Adverse Event Form. Protocol-related AEs and SAEs will be collected from the time the participant has consented to study participation.

SAEs considered related to study drug may be reported at any time, even after the participant's final treatment visit.

The reporting of laboratory abnormalities as both laboratory findings and AEs should be avoided. Laboratory abnormalities should not be reported as AEs unless any one of the following are met:

- Any criterion for an SAE is fulfilled
- The laboratory abnormality causes the participant to discontinue from the study treatment
- The laboratory abnormality causes the participant to interrupt the study treatment
- The laboratory abnormality causes the participant to modify the dose of study treatment
- The laboratory abnormality requires intervention
- The PI (or designee) determines the laboratory value as an abnormal change from baseline and is of clinical significance for that participant
- Laboratory values consistent with the DAIDS designation of Grade 3 (events as severe or medically significant) and Grade 4 (events as life-threatening), should be reported as AEs or SAEs, as appropriate.

12.1 Definitions

12.1.1 Adverse Event

AE means any untoward medical occurrence in a participant or clinical trial participant associated with the use of a drug in humans, whether or not considered drug related. An adverse event can therefore be any unfavorable and unintended sign (including an abnormal laboratory finding, for example, see **Section 12.2.1**), symptom or disease temporally associated with the use of a medicinal product, whether or not considered related to the medicinal product.

This includes any occurrence that is new in onset or aggravated in severity or frequency from the baseline condition, or abnormal results of diagnostic procedures, including laboratory test abnormalities.

12.1.2 Adverse Drug Reaction

Adverse drug reaction (ADR) is a noxious and unintended response to the medicinal product related to any dose. As used herein, the phrase "response to a medicinal product" means that a causal relationship between a medicinal product and an AE is at least a reasonable possibility.

12.1.3 Adverse Event of Special Interest

An AE of special interest (AESI) is an event of scientific and medical interest or concern to the sponsor, for which ongoing monitoring and rapid communication to the sponsor could be appropriate. It may be a serious or non-serious AE, which may require further investigation in order to characterize and understand it.

12.1.4 Attribution/Assessment of Causality

Attribution/Assessment of Causality is a determination that describes the relationship or association of the study drug with an adverse event.

This assessment of causality or relationship of AEs to the study drug is provided by the PI and is determined by 1) temporal relationship of the event to the administration of study drug; 2) whether an alternative etiology has been identified, and 3) biological plausibility.

The causality assessment categories that will be used for this study are described below.

Causality assessments that are considered **not related** to study drug:

Not related: The event is related to an etiology other than the study drug (the alternative etiology must be documented in the participant's medical record).

Unlikely: The event is unlikely to be related to the study drug and likely to be related to factors other than study drug. An alternate explanation is more likely (e.g., concomitant drugs, concomitant disease), or the relationship in time suggests that a causal relationship is unlikely.

If an AE or SAE is considered "unlikely" or "unrelated" to study drug, the PI should offer his/her clinical opinion as to what factor(s), agent(s), or process(s) were the likely causative mechanism for the event.

Causality assessments that are considered **related** to study drug:

Possible: There is an association between the event and the administration of the study drug and there is a plausible mechanism for the event to be related to study drug; but there may also be alternative etiology, such as characteristics of the participant's clinical status or underlying disease.

Probable: There is an association between the event and the administration of study drug, a plausible mechanism for the event to be related to the study drug and the event could not be reasonably explained by known characteristics of the participant's clinical status or an alternative etiology is not apparent.

Definite: There is an association between the event and the administration of study drug; a plausible mechanism for the event to be related to the study drug, causes other than the study drug have been ruled out, and/or the event re-appeared on re-exposure to the study drug.

12.1.5 Serious Adverse Events

An SAE is any AE that results in any of the following outcomes:

- Death
- Life-threatening (immediate risk of death)
- Inpatient hospitalization for longer than 24 hours or prolongation of existing hospitalization (even if the event is Grade 1)
- Persistent or significant disability or incapacity
- Congenital anomaly/birth defect
- Important medical events

12.1.6 Severity Criteria

Event *severity* will be assigned according to the assessment of the PI using Division of AIDS (DAIDS) grading table Version 2.1.

Severity Grade for Parameters Not Identified in the Grading Table:

The functional table below should be used to grade the severity of an AE that is not specifically identified in the grading table. In addition, all deaths related to an AE are to be classified as Grade 5.

PARAMETER	GRADE 1 MILD	GRADE 2 MODERATE	GRADE 3 SEVERE	GRADE 4 POTENTIALLY LIFE- THREATENING
Clinical adverse event NOT identified elsewhere in the grading table	Mild symptoms causing no or minimal interference with usual social & functional activities with intervention not indicated	Moderate symptoms causing greater than minimal interference with usual social & functional activities with intervention indicated	Severe symptoms causing inability to perform usual social & functional activities with intervention or hospitalization indicated	Potentially life-threatening symptoms causing inability to perform basic self-care functions with intervention indicated to prevent permanent impairment, persistent disability, or death

